### **CONCEPTUAL MODEL AND STUDY HYPOTHESES**

The Stress Process Model (SPM) for Caregivers was the conceptual model used for the study premise and for selecting measures and study hypotheses. The SPM has been widely used in research on stress and coping for caregivers. The domains of the SPM include: 1) Background and Care Context, 2) Objective and Subjective Stressors, 3) Coping and Social Support Resources, 4) Secondary Stressors: Role and Intra-Psychic Strain, and 5) Psychosocial Well-Being Outcomes. Prior studies extend the SPM's category of "coping and social support" to include interventions. For the current study, the *Kinto Care Coaching Intervention* was conceptualized as such in improving outcomes for caregivers. The SPM guided study hypotheses that included hypothesized significant improvements for participants in the intervention condition as compared to participants in the waitlist control condition for the following secondary stressors and psychosocial well-being outcomes : Unmet Needs; Unmet Needs Distress; Financial Self-Efficacy; Dyadic Relationship Strain and Role Captivity; Emotional Health Strain; Caregiver Mastery; Personal Gain; Loneliness; Caregiver Burden; Anxiety Symptoms; and Depressive Symptoms. Exploratory hypotheses also were examined and included measures of Instrumental Activities of Daily Living (IADL)/Personal Activities of Daily Living (PADL) Difficulty; IADL/PADL Distress; Cognitive Difficulty; Cognitive Distress; Behavioral Frequency; and Behavioral Distress.

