### **DESIGN AND PROCEDURES**

A randomized controlled trial research design was used to examine the efficacy of the *Kinto Care Coaching Intervention*. After consenting to participate in the study, caregivers completed the baseline/Time 1 survey and were then randomly assigned to the intervention condition or the waitlist control condition. Participants in the intervention condition received the *Kinto Care Coaching Intervention* that used technology via a mobile app to implement the 6-week structured protocol that consisted of the following: 1) initial assessment of care needs; 2) an initial one-on-one virtual care coaching meeting that developed an Action Plan that included both financial and caregiver support goals; 3) interactive and on-going support and educational resources through the mobile app; 4) access

to support groups; and 5) on-going chat groups, with both their care coach and support group peers. Participants randomly assigned to the waitlist control condition were eligible to receive a modified version of the intervention after completion of the study.

To examine intervention efficacy, outcomes were assessed across time that included both short-term and long-term impacts. In total, participants completed 3 surveys: Time 1 (Baseline); Time 2 (after program completion); and Time 3 (45 days after Time 2). All evaluation surveys were completed via Survey Monkey. Once participants completed all 3 of the evaluation surveys, they received a \$120.00 gift certificate as compensation for their time.

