### **Primary Analyses:**

To examine intervention efficacy, outcomes were assessed across time that included both short-term and long-term impacts. Separate 2 (condition: intervention, waitlist control) x 3 (time: Time 1, Time 2, Time 3) repeated measures general linear models were used to examine mean group differences across time between the intervention and waitlist control groups for each outcome measure. The repeated measures analyses indicated whether there was any significant change across time for each outcome measure based on whether participants received the intervention or had not received the intervention. Employment status was included as a covariate in all analyses to control for the significant difference found at baseline between the two conditions. For significant outcomes that did not meet the Sphericity assumption, the Greenhouse-Geisser correction was used and reported for degrees of freedom. For outcome measures that were found to be significant, additional post-hoc pairwise comparison with a Bonferroni correction were conducted to examine where the change occurred across the different data collection periods (i.e., Time 2, Time 3).

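### None of the 11–12 efficacy outcomes is named primary and there is no correction across them: with no true effects, the chance of at least one significant result is about 22–40% (assuming alpha 0.05 and correlations of 0.7 to 0.3)

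*Combined protocol and SAP*

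**What the plan says.** The aim is efficacy. Design and Procedures states: "A randomized controlled trial research design was used to examine the efficacy of the" intervention. The SAP repeats the aim under Primary Analyses: "To examine intervention efficacy, outcomes were assessed across time that included both short-term and long-term impacts".

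The outcomes are set out in Conceptual Model and Study Hypotheses as "hypothesized significant improvements for participants in the intervention condition as compared to participants in the waitlist control condition". They form one unranked list. It begins "Unmet Needs; Unmet Needs Distress; Financial Self-Efficacy; Dyadic Relationship Strain and Role Captivity; Emotional Health Strain; Caregiver Mastery; Personal Gain; Loneliness" and ends "Loneliness; Caregiver Burden; Anxiety Symptoms; and Depressive Symptoms". A further six measures are set apart: "Exploratory hypotheses also were examined and included measures of Instrumental Activities of Daily Living" and related scales.

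Under Primary Analyses, separate 2 x 3 analyses are described: "repeated measures general linear models were used to examine mean group differences across time between the intervention and waitlist control groups for each outcome measure". Each outcome is judged on its own model, which "indicated whether there was any significant change across time for each outcome measure". The heading Primary Analyses covers the models for every outcome and does not select a primary one. Two corrections are mentioned. Greenhouse-Geisser deals with sphericity. Bonferroni applies to post-hoc pairwise comparisons over time, and only for outcomes already significant. The text gives no alpha, no ordering of outcomes and no adjustment across them.

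**The concern.** With 11–12 outcomes each tested separately, some will often reach significance by chance. A named primary outcome, a correction across outcomes, or a rule for what pattern of results supports efficacy would guard against over-reading such results. The supplied text has none of the three. One or two significant scales could then be presented as showing that the programme works, and a reader cannot tell from the plan what result would have counted as failure. The effect estimates stay usable. What suffers is the overall efficacy claim, for which unadjusted p-values overstate the evidence.

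**Working it through.** **Inputs from the documents**
- Number of hypothesised outcomes, k. The first quoted part of the list has 8 entries and the second has 4, with Loneliness in both: 8 + 4 − 1 = 11. Counting Dyadic Relationship Strain and Role Captivity separately gives 12.
- Test per outcome: condition by time in a 2 x 3 model, with (2 − 1)(3 − 1) = 2 numerator degrees of freedom.

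**Assumptions (not in the documents)**
- Alpha is 0.05 per outcome, and no outcome has a true effect.
- The test statistics have equal pairwise correlation r. The outcomes are related strain and well-being scales, so 0.3 to 0.7 is the working range. Independence is an upper reference.

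The plan states no error rate, so there is no figure of its own to reproduce.

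**Step 1: at least one significant outcome.** If the outcomes were independent, 1 − 0.95^11 = 0.431 and 1 − 0.95^12 = 0.460. For correlated two-sided tests with c = 1.96,

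P = 1 − ∫ [Φ((c − √r·x)/√(1−r)) − Φ((−c − √r·x)/√(1−r))]^k φ(x) dx.

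The 2-df test was simulated with 1,000,000 draws per setting.

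| r | 1-df integration, k = 11 / 12 | 2-df simulation, k = 11 / 12 |
|---|---|---|
| 0.3 | 0.375 / 0.397 | 0.378 / 0.401 |
| 0.5 | 0.304 / 0.319 | 0.311 / 0.327 |
| 0.7 | 0.223 / 0.232 | 0.232 / 0.240 |

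The range is 22–40%, with 30–33% at r = 0.5.

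**Step 2: at least two significant outcomes (2-df simulation).** 0.117 / 0.131 at r = 0.3, 0.123 / 0.134 at 0.5 and 0.117 / 0.124 at 0.7, so about 12–13%.

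**Step 3: a favourable result that also passes the post-hoc step.** The rule is a 2-df p below 0.05 together with a favourable between-arm contrast at Time 2 or Time 3 with two-sided p below 0.05/2 = 0.025. The Time 2/Time 3 correlation is assumed to be 0.5.

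| r | k = 11 / 12 |
|---|---|
| 0 | 0.181 / 0.195 |
| 0.3 | 0.148 / 0.158 |
| 0.5 | 0.121 / 0.128 |
| 0.7 | 0.090 / 0.093 |

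One outcome alone under this rule gives 0.018. The ratios run from 0.090/0.018 = 5.0 to 0.158/0.018 = 8.8. With a Time 2/Time 3 correlation of 0.3 to 0.7, the range over r = 0.7 to 0.3 is 8–17%.

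**Step 4: sensitivity to alpha, r = 0.7 to 0.3.** The step 1 figure is 6–10% at alpha 0.01 and 38–64% at 0.10. The step 3 figure is 2–4% and 16–29%.

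**Step 5: after Holm at 0.05.** With no true effects, Holm rejects something only if the smallest p is at or below 0.05/k: 0.05/11 = 0.0045 or 0.05/12 = 0.0042. The step 1 figure falls to 0.045 at r = 0.3 and 0.028–0.030 at r = 0.7. The step 3 figure falls to 0.021 and 0.014.

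**The case against.** - **The 22–40% counts results in either direction.** The hypotheses concern improvement, so the harm described needs a favourable result. This is fair: 9–16% is the figure closest to a false efficacy claim. It is still about 5 to 9 times the rate for one outcome under the same rule.
- **Alpha and the correlations are assumed.** This is also fair. At r = 0.9 the step 1 figure drops to about 13% and the step 3 figure to about 5%. Lower correlations raise both.
- **The post-hoc wording is ambiguous.** It may mean comparisons within each arm, or all three pairs of time points. A three-comparison threshold on the same contrasts gives about 8–14% instead of 9–16%. Within-arm comparisons are not covered by step 3. Steps 1 and 2 do not depend on this reading, because they concern the test that comes before the post-hoc step.
- **The plan never says that one significant outcome proves efficacy.** For a claim about a single named construct, the outcome-level test keeps its nominal error rate. That is correct. The difficulty arises when an overall efficacy conclusion is drawn from whichever outcomes succeed. Efficacy is the stated aim, and the plan gives no rule against doing so.
- **A primary outcome may be recorded elsewhere.** The supplied text omits one opening portion, so this cannot be excluded. The hypotheses, design and analysis sections are present and name none.
- **Any correction is now retrospective, and Holm is one choice among several.** The plan is written in the past tense, with the baseline imbalance already known. This calls for disclosure but does not remove the need for a rule.

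**Conclusion.** The concern holds. In the documents supplied, 11–12 hypothesised outcomes stand on an equal footing, each is tested separately, and nothing controls error across them. The post-hoc Bonferroni removes some chance favourable claims but gives no formal control across outcomes. With no true effects, alpha 0.05 and correlations of 0.7 to 0.3, at least one significant outcome is expected about 22–40% of the time and at least two about 12–13%. A favourable one that passes the post-hoc step is expected about 9–16% of the time, if that step means two between-arm contrasts. The exact size depends on these assumptions; the absence of a primary outcome and of any correction across outcomes does not.

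**What to change.** - Apply Holm across the 11–12 condition-by-time tests. Declare an outcome significant only on its adjusted p-value (smallest p against 0.0045 for 11 outcomes or 0.0042 for 12), and run post-hoc comparisons only for those outcomes.
- State the alpha, and whether Dyadic Relationship Strain and Role Captivity are one scale or two.
- Name a primary outcome, tested first at 0.05 with Holm on the rest, only if it was fixed before data were seen.
- If the correction was chosen after results were known, say so and show unadjusted p-values alongside.
- Report the six exploratory measures as estimates with confidence intervals and make no efficacy claim from them.

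The cost is SAP wording and adjusted p-values from models already run, with no new data or design change. The downside is that some nominally significant outcomes may lose significance, and Holm is stricter than false discovery rate control.

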## **II. Statistical Analyses Plan**

### **Preliminary Data Analyses:**

Data were cleaned including examining missing data and addressing any out-of-range values. All Time 1 measures were tested for reliability using Cronbach's alpha, with alphas equal to or greater than .70 demonstrating good reliability. Independent t-tests, one-way ANOVAs, and chi square tests were conducted to ensure random assignment resulted in equivalent groups between the intervention and waitlist control conditions on select demographic and caregiving characteristics and to identify covariates to include in subsequent analyses. With respect to attrition analyses, independent t-tests, one-way ANOVAs, and chi-square tests were used to examine if there were any significant differences on select demographic and caregiving characteristics and the Time 1 scale scores for each outcome between participants who completed the study protocol and those who did not.

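### Covariates were chosen by significance tests of baseline balance, the only stated reason for adjusting every model for employment status; that p-value does not show whether a variable predicts change

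*Combined protocol and SAP*

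**What the plan says.** Under Preliminary Data Analyses, the SAP compares the arms with t-tests, one-way ANOVAs and chi-square tests. The tests have two purposes. The first is "to ensure random assignment resulted in equivalent groups between the intervention and waitlist control conditions on select demographic and caregiving characteristics"; the second is "to identify covariates to include in subsequent analyses". The variables screened, their number and the significance threshold are not given. Time 1 outcome scores are named in the attrition comparison ("and the Time 1 scale scores for each outcome between participants who completed the study protocol and those who did not") but not in the comparison of arms.

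Under Primary Analyses, each outcome has a 2 (condition) x 3 (time) repeated measures general linear model. The covariate statement is: "Employment status was included as a covariate in all analyses to control for the significant difference found at baseline between the two conditions". No model without employment is described, and the section does not say whether employment was crossed with time.

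On the order of events, Design and Procedures states that "caregivers completed the baseline/Time 1 survey and were then randomly assigned to the intervention condition or the waitlist control condition".

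**The concern.** Baseline data were collected before allocation. If randomisation was sound and everyone randomised was tested (the second is not stated), any significant baseline difference is chance. Its p-value measures how uneven the split happened to be. It carries no information on whether the variable is related to change in the outcome, which is what makes a covariate useful for the condition-by-time test.

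A rule built on that p-value can go wrong in two ways. It can admit a variable unrelated to change. It can also leave out a variable that predicts change because the arms were similar on it, or differed by slightly too little to reach significance. The first costs little. The second gives up precision and, after a near-miss imbalance, leaves some bias in that particular trial.

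**Working it through.** The documents give no sample size, alpha, allocation ratio, number of baseline tests or correlations, so there is no planned figure to reproduce. Everything below is illustrative: two-sided 0.05 and equal arms, with other assumptions as shown.

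**1. How easily the screen picks something up by chance.** For k independent tests at 0.05, the probability of at least one significant difference is 1 − 0.95^k:
- k = 5: 0.226
- k = 10: 0.401
- k = 15: 0.537

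One significant difference is therefore unremarkable under correct randomisation.

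**2. Cost of adjusting for a two-level employment variable unrelated to change.** With imbalance z, the standard error rises by a factor of about √(1 + z²/(N − 2)), ignoring the lost degree of freedom. At z = 1.96:
- N = 200: 1.010
- N = 100: √(1 + 3.84/98) = 1.019
- N = 60: 1.033
- N = 40: 1.049

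This cost is small.

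**3. Cost of leaving out a predictor of change, for the planned test.** This is a simulation of the 2-df condition-by-time F test. Sphericity holds, the effect and the covariate both act on the follow-up-minus-baseline contrast, the covariate is crossed with time, and unadjusted power is set to 0.80. The rule adjusts only when the baseline test has p < 0.05. The correlation of the covariate with change is r.

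| N | r | Power, balance-test rule | Power, always adjusted | Difference (points) |
|---|---|---|---|---|
| 60 | 0.3 | 0.801 | 0.820 | 1.9 |
| 100 | 0.3 | 0.796 | 0.817 | 2.1 |
| 60 | 0.5 | 0.805 | 0.863 | 5.8 |
| 100 | 0.5 | 0.810 | 0.872 | 6.2 |

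Monte Carlo error is about 0.005 on each power. A separate simulation of the same test gave about 2 to 3 points at r = 0.3 and 5 to 6 at r = 0.5. At r = 0.1 the large-sample figures for a single contrast are 0.8005 under the rule and 0.8039 if always adjusted, which is almost no difference.

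**4. Type I error.** Over all trials, the large-sample rate under the rule is 0.0497, 0.0476 and 0.0432 at r = 0.1, 0.3 and 0.5. The rule is slightly conservative, not inflated.

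**5. Near-miss imbalance.** The probability that |z| lies between 1.5 and 1.96 is 2 × (Φ(1.96) − Φ(1.5)) = 0.084 for a given variable. Conditional on z, the unadjusted statistic is N(rz, 1 − r²) under the null. Averaged over that window, rejection is 5.2%, 6.9% and 10.1% at r = 0.1, 0.3 and 0.5.

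**6. Not adjusting for a covariate that is significantly unbalanced.** The same formula averaged over |z| > 1.96 gives unadjusted rejection under the null of 9.8% at r = 0.3 and 18.5% at r = 0.5. The adjusted test stays at about 5%. This bears on how a model without employment should be read.

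**7. Dependence on how the covariate entered.** In one simulated complete three-wave dataset (N = 60), adding employment as a main effect only left the two condition-by-time estimates at 0.357 and 0.300 (SE 0.387), identical to the unadjusted model. With an employment-by-time term they became 0.307 and 0.206 (SE 0.400). Steps 2, 3, 5 and 6 therefore apply to the condition-by-time test only where the covariate is crossed with time.

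**The case against.** The strongest reply is that the harm is hypothetical. The documents do not show that any predictor of change was left out. The screened variables are unlisted and may have been shortlisted on conceptual grounds: the protocol states that "The Stress Process Model (SPM) for Caregivers was the conceptual model used for the study premise and for selecting measures and study hypotheses", although it does not say that the screened variables came from that model. The power loss needs correlations of 0.3 to 0.5 with change, which nothing in the documents supports. Time 1 scores already enter the model as a time level. If employment entered only as a between-subject main effect, then with complete data it cannot have altered the condition-by-time result at all. All of this stands, and it makes the cost conditional.

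The reply does not rescue the rule itself. A balance test remains the wrong instrument for choosing covariates whatever it happened to select, and without the screened list, the threshold or the form of the covariate term, a reader cannot judge what it did here.

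Three stronger readings are tempting, and the documents do not support them:
- A reader might infer that employment is in the models for no reason other than imbalance. Imbalance is the only reason stated; an unstated one is not excluded.
- A reader might infer that adjusting for employment was a mistake. It may well be prognostic for outcomes such as Financial Self-Efficacy or Role Captivity, and given the imbalance adjustment would then be protective.
- A reader might infer that choosing a covariate from the data raised the false-positive rate. Step 4 shows that it does not.

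**Conclusion.** The selection rule is poorly founded, and the SAP's own wording establishes that it was used. Its consequence for this trial cannot be determined from the documents. If a predictor of change was left out for lack of a significant imbalance, the planned test gave up about 2 to 3 points of power at r = 0.3 and about 5 to 6 at r = 0.5, from a base of 0.80, and almost nothing at r = 0.1. That rests on assumed N, alpha and correlations, on sphericity, and on covariates crossed with time. No efficacy result is shown to be invalid. The point is minor to moderate.

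**What to change.** Keep the employment-adjusted analysis on record as performed. In a short dated addendum:

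1. List the variables screened and the threshold, and state whether covariates were crossed with time.
2. Stop giving balance tests as the reason for choosing covariates.
3. For every outcome, add an analysis of Time 2 and Time 3 adjusted for that outcome's own Time 1 score plus a short covariate set chosen on prognostic grounds. Employment may qualify. Fix the set in writing, once for all outcomes, before the added models are run.
4. Show the model without employment only as a sensitivity result. State that a difference does not discredit the adjusted result: with this imbalance, the unadjusted model is the worse one if employment is prognostic.
5. Put everything in one table, label the additions post hoc, and say for each outcome whether the conclusion differs.

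The cost is a re-run on existing data. The hypotheses section lists 11 hypothesised and 6 exploratory items, so three results each gives at least 17 × 3 = 51 result sets; a single table limits selective emphasis. Choosing covariates after the results are known leaves some analyst freedom, and the added models carry only post hoc weight.

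### The only step that separates short-term from later impact appears to compare survey times rather than arms; the timing of any effect should rest on between-arm contrasts of change at Time 2 and Time 3

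*Combined protocol and SAP*

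**What the plan says.** The section Conceptual Model and Study Hypotheses states the hypotheses between arms: "hypothesized significant improvements for participants in the intervention condition as compared to participants in the waitlist control condition". Design and Procedures and the SAP's Primary Analyses both make short-term and long-term impact aims of the evaluation, with surveys at baseline (Time 1), after the programme (Time 2) and 45 days later (Time 3).

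For the overall test, Primary Analyses says "Separate 2 (condition: intervention, waitlist control) x 3 (time: Time 1, Time 2, Time 3) repeated measures general linear models were used" and gives the purpose as "to examine mean group differences across time between the intervention and waitlist control groups for each outcome measure". The result is read as showing "whether there was any significant change across time for each outcome measure based on whether participants received the intervention".

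For the follow-up, which applies only to outcomes found significant, it says: "additional post-hoc pairwise comparison with a Bonferroni correction were conducted to examine where the change occurred across the different data collection periods". Time 2 and Time 3 are given in parentheses. The text does not name the model term that makes an outcome significant, the pairs compared, or the arm in which they are compared.

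**The concern.** An overall 2 x 3 test can show that the arms follow different courses. It cannot say whether they differ at Time 2, at Time 3 or at both. Only the follow-up step can, so the short-term and long-term conclusions depend on it.

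As worded, that step looks for change between surveys. A within-arm change adds the programme effect to whatever both arms share, such as adaptation or the effect of repeating the survey. A change pooled over arms does not isolate the programme at all. Neither is a randomised comparison. Noting that change was significant in one arm and not in the other is not a test of the difference between arms.

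Two errors can follow for an outcome with a real effect:

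- Shared change can make the programme appear to work at a survey where the arms do not differ.
- An effect that consists of waitlist caregivers worsening while intervention caregivers hold steady does not show in the intervention arm's own comparisons.

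**Working it through.** **Inputs.** From the documents: two arms, three surveys, one model per outcome, Bonferroni-corrected pairwise comparisons. The documents state no sample size, SD, effect size or correlation, so there is no figure of the plan's own to reproduce. Assumed: n = 30, 50 or 100 per arm; SD 1; correlation ρ = 0.5 or 0.7 between any two surveys; normal data; no dropout; employment covariate omitted; overall test at 5%. Three survey times give three pairs, so time comparisons are taken at 0.05/3.

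**Scenario 1: shared change, effect at Time 2 only.** Both arms improve by 0.3 SD at Times 2 and 3, and the arms truly differ by 0.5 SD at Time 2 only. For Time 1 to Time 3:

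- Expected intervention-arm change = shared + effect = 0.3 + 0 = 0.3.
- Expected between-arm difference in change = 0.3 − 0.3 = 0.
- SE of a within-arm change = √(2(1 − ρ)/n).
- SE of the between-arm difference in change = √(4(1 − ρ)/n).

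Smallest setting (n = 30, ρ = 0.5): within-arm SE = √(1/30) = 0.183, and 0.3/0.183 = 1.64. The critical t is 2.54, so the noncentral t distribution gives about a 20% chance of significance. Largest setting (n = 100, ρ = 0.7): SE = √(0.6/100) = 0.0775, and 0.3/0.0775 = 3.87. The critical t is 2.435, giving about 92%.

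Simulation restricted to trials with a significant condition x time test gives, over all settings:

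| Finding at Time 3, where the arms do not differ | Share of trials |
|---|---|
| Intervention arm's Time 1–3 change significant (0.05/3) | 23–92% |
| Significant there but not in the waitlist arm | 7–25% |
| Between-arm contrast of change significant (0.05/2) | 2–4%; 5% at n = 30, ρ = 0.5 on a repeat run |

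Conditioning on the overall test moves the 20% only to 23% and leaves the 92% unchanged. A significant interaction therefore does little to make the within-arm comparison point to the right survey.

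A mirror case gives the same pattern (shared 0.4 SD, true 0.5 SD effect at Time 3 only). The effect is wrongly placed at Time 2 in 41% to nearly 100% of trials by within-intervention comparisons, 75–100% by comparisons pooled over arms, and 2–6% by the between-arm contrast.

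**Scenario 2: protective effect.** The waitlist arm worsens by 0.4 SD at Times 2 and 3, and the intervention arm is stable. After a significant condition x time test:

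- the intervention arm's own comparisons flag Time 2 or Time 3 in 2–5% of trials;
- the waitlist arm's own comparisons flag worsening in 84–100%;
- the direct contrasts flag a difference in 86–99%, even at the stricter 0.05/3.

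**Scenario 3: shared change, no arm effect.** With a shared 0.4 SD change, the condition x time test is significant in about 5% of trials, which is its nominal level.

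**The case against.** The strongest reply is that the follow-up sentence names no arm. Its parenthesis lists only Time 2 and Time 3, whereas comparing survey times would also need Time 1. It could therefore mean arm means compared at each follow-up survey. That would be a valid randomised comparison: a chance Time 1 difference costs precision but does not undo randomisation. At ρ = 0.5 the change score has variance 2(1 − 0.5) = 1, the same as the follow-up score. In scenario 1, arm means falsely flag Time 3 in only 1.2–2.2% of trials at 0.05/3, so on this reading the timing harm disappears. This stands as a possible reading, but a less natural one, because the stated aim is to locate change across periods. The plan does not settle it.

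Three stronger inferences are tempting, and the documents do not support them:

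- **Change shared by both arms would by itself be reported as a programme effect.** The overall test is described as examining group differences over time and is read according to receipt of the intervention. That describes condition x time, which shared change passes in only about 5% of trials.
- **An outcome could qualify on the time main effect.** Under that rule a shared 0.2–0.3 SD change would qualify in 33–100% of trials. The term is not named, so the plan does not formally exclude this, but the full sentence points the other way. The figure is not a consequence of the plan.
- **A protective effect would be missed altogether.** It can still pass the overall test (48–100% of trials for a 0.5 SD worsening), and nothing confines the comparisons to the intervention arm. Worsening in the waitlist arm would usually be seen there, though that is still not a test between arms.

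**Conclusion.** The point holds as one about timing and attribution. On its most natural reading, the only step able to separate short-term from long-term impact compares survey times, and no between-arm contrast at either follow-up survey is planned, although the hypotheses are between arms. It does not show that the overall efficacy test is invalid.

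The 23–92% applies if only the intervention arm is examined. If both arms are examined and the pattern of significance is compared, the figure is 7–25%. The direct contrast errs in about 2–5%. These figures show direction and rough size under assumed sample sizes, correlations and effects; they are not estimates for this trial. The change is worth making, with medium confidence because the sentence can be read in more than one way.

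**What to change.** In Primary Analyses:

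1. State that the condition x time effect, and no other term, makes an outcome significant.
2. For each such outcome, replace the pairwise time comparisons with two between-arm contrasts from the same model: intervention minus waitlist in change from Time 1 to Time 2, and in change from Time 1 to Time 3. Test each at 0.05/2 = 0.025 and report confidence intervals.
3. Base the short-term statement on the first contrast and the long-term statement on the second.
4. Show within-arm changes as description, without significance claims.

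If the comparisons already made were of arms at each survey, say so explicitly.

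The plan is written in the past tense, so this means re-reporting. It needs contrast statements in a model already fitted and no new data. Some statements of significant change within an arm would be lost.
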